5 CORRELATIVE STUDIES

5.1 SUMMARY

This study will attempt to use rhIL-15 to increase NK cell number and activity, thereby enhancing the ADCC of mogamulizumab in treatment of patients with relapsed and refractory MF/SS and ATLL. ADCC capacity of ex vivo PBMCs will be tested on CCR4-expressing cell lines before, during, and after protocol treatment. CCR4 mutation status will be determined for each patient by batch processing, and correlated with response and survival. Differences in circulating immune cell subsets associated with administration will be followed throughout treatment to both study the effects of combined rhIL-15/mogamulizumab therapy on the immune system, and to identify potential biomarkers that would be predictive of response. With the same goal in mind, immune cell subsets in the tumor microenvironment before and after treatment will be determined using single-cell RNA sequencing.

Sample	Collection Details*	Time Points							Supervising Laboratory/Investigator
		Baseline	C1 D8	C1 D15	C2-6 D1	C2-6 D15	Follow-up [#]		
Blood Samples									
Lymphocyte subset testing	• 2 x 10mL K ₂ EDTA (lavender-top) tubes	X	X	(X)	(X)	(X)	(X) ¹	Immunology section, NIH CC	
ADCC of mogamulizumab	• 3 x 10mL sodium heparin green-top tubes	(X) ²	(X) ²					[name]	
Tissue immune cell subsets (comparison)	• 1 x 5mL sodium heparin green-top tube	(X)		(X)			(X)	[name]	

Abbreviated Title: IL-15+Mogamulizumab**Version Date:** 11/16/2020

Sample	Collection Details*	Time Points						Supervising Laboratory/ Investigator
		Baseline	C1 D8	C1 D15	C2-6 D1	C2-6 D15	Follow-up [#]	
Circulating tumor DNA, plasma banking	• 1 x 10mL K ₂ EDTA tube • 1 x 10mL Streck/BCT tube	X	(X)	X	(X)	(X)	X ³	[name] (Leidos CSL)
PBMC banking	• 2 x 10mL sodium heparin green-top tubes	X	X	X	X	X	X	
Anti-IL-15 antibodies	• 1 x 4mL SST tube	X			X		X ¹	
CCR4 expression	• 2 x 10mL sodium heparin green-top tubes	(X)	(X)		(X)			[name] (Laboratory of Pathology)
CCR4 mutation status	• 2 x 10mL sodium heparin green-top tubes	(X)						
Tissue Samples								
CCR4 expression	• One core biopsy sample in formalin	X**		(X)				[name] (Laboratory of Pathology)
CCR4 mutation status	• One core biopsy sample in formalin	X**		(X)				[name] (Laboratory of Pathology)
Tissue immune cell subsets	• Two core biopsy samples in RPMI 1640 with 10% human serum and antibiotics • One core biopsy sample in formalin NOTE: Samples may be tumor tissue or bone marrow aspirate/biopsy	X**		(X)			(X)	[name] (Laboratory of Pathology)
Single-cell RNA-Seq	• One core biopsy sample in RPMI 1640 with 10% human serum and antibiotics	(X)		(X)				[name] (Laboratory of Pathology) and CCR single cell core
Other Samples								
Germline DNA	• Blood, Buccal Swab, or Saliva (preferred)	X						[name] (Leidos CSL)

Abbreviated Title: IL-15+Mogamulizumab

Version Date: 11/16/2020

Sample	Collection Details*	Time Points						Supervising Laboratory/ Investigator		
		Baseline	C1 D8	C1 D15	C2-6 D1	C2-6 D15	Follow-up [#]			
(X) = Optional; samples will be collected if adequate time/staff available for processing. If an optional sample is not collected at baseline, it would also not be collected in follow-up unless specifically requested by the PI.										
*Tubes/media may be adjusted at the time of collection based upon materials available or to ensure the best samples are collected for planned analyses.										
** Tumor biopsy is required if archival tissue is not available or adequate; otherwise, this is optional										
#Subjects who discontinue treatment for a reason other than disease progression and who do not start new treatment should continue to have study bloods collected at the scheduled time points.										
¹ At the end of treatment only.										
² For ADCC of mogamulizumab, Baseline and C1D8 samples should be collected for at least one patient per dose level, and for at least three patients at the MTD										
³ At each follow-up visit prior to disease progression, as specified in Section 3.6.2 .										

Note: If there is an optional biopsy for research in the protocol, then the patient will consent at the time of the procedure. If the patient refuses the optional biopsy at that time, the refusal will be documented in the medical record and in the research record.

5.2 SAMPLE COLLECTION AND PROCESSING

5.2.1 Summary

The planned analyses described below may be done on leftover and/or shared sample portions from the respective laboratories, as needed. In addition to the prospectively collected samples below, leftover portions of samples sent for routine laboratory testing (e.g., plasma from CBC/hematologies) may also be retrieved for research tests prior to being discarded. The planned prospective analyses are identified below; laboratories may share resources or collaborate on analyses, if appropriate.

Portions of all samples may be banked for future research analyses; prospective consent will be obtained during the informed consent process.

The blood drawing limits for research purposes are as follows:

- For adult subjects: The amount of blood that may be drawn from adult patients for research purposes shall not exceed 10.5 mL/kg or 550 mL, whichever is smaller, over any eight-week period.

Unless otherwise noted, Lymphoid Malignancies Branch Clinical Research personnel will use courier or escort service to arrange delivery of samples to destinations listed in subsections below.

5.2.2 Blood Samples

All blood samples will be drawn by NIH Clinical Center phlebotomy, inpatient unit, outpatient clinic, or day hospital staff.

5.2.2.1 Lymphocyte subset testing by flow cytometry (FACS)

- Collect blood in EDTA tubes; gently invert tubes 8-10 times immediately after collection

Abbreviated Title: IL-15+Mogamulizumab

Version Date: 11/16/2020

- Labels listing the patient's name, date of birth, date and time of the blood draw will be affixed to all the tubes by the staff person who obtained the samples.
- Lymphoid Malignancies Branch Clinical Research personnel will arrange for these samples to be delivered to: Immunology Lab, NIH Clinical Center [name]. If the Immunology Section Laboratory is unable to perform this analysis on the specified days, this assessment maybe omitted or replaced with standard TBNK panel.

5.2.2.2 Antibody-dependent cell cytotoxicity (ADCC) of mogamulizumab

- Collect blood in sodium heparin tubes; gently invert tubes 8-10 times immediately after collection.
- Lymphoid Malignancies Branch Clinical Research personnel will arrange for these samples to be delivered to Clinical Support Laboratory, Leidos Biomedical Research, Inc.in Frederick, MD, for processing per established laboratory techniques, storage, and batch analysis by the [name] Laboratory.

5.2.2.3 Cell-free DNA (cfDNA), circulating tumor DNA (ctDNA) and plasma banking

- Collect 10 mL of blood in one cell-free DNA (e.g., Streck BCT/collection tubes) and 10 mL of blood in one K2EDTA tube; gently invert the tubes 8-10 times immediately after collection.
- Labels listing the patient's name, date of birth, date and time of the blood draw will be affixed to all the tubes by the staff person who obtained the samples. Plasma will be isolated and frozen at -80°C until analysis (e.g., centrifuged at 1800 x g for 10 minutes at room temperature; plasma transferred/frozen in aliquots of 1.5-2 mL each).
- Lymphoid Malignancies Branch Clinical Research personnel will arrange for these samples to be delivered to Clinical Support Laboratory, Leidos Biomedical Research, Inc.in Frederick, MD for sample processing per established techniques maintained within standard operating procedures in the laboratory.

5.2.2.4 PBMC banking and tissue immune cell subsets (comparison)

- Collect blood in sodium heparin tubes; gently invert tubes 8-10 times immediately after collection.
- Lymphoid Malignancies Branch Clinical Research personnel will arrange for these samples to be delivered to Clinical Support Laboratory, Leidos Biomedical Research, Inc.in Frederick, MD for sample processing per established techniques maintained within standard operating procedures in the laboratory.

5.2.2.5 Anti-IL-15 antibody testing

- Collect blood in a 4mL SST tube; gently invert tubes 8-10 times immediately after collection.
- Lymphoid Malignancies Branch Research personnel will arrange for these samples to be delivered to Clinical Support Laboratory, Leidos Biomedical Research, Inc.in Frederick, MD, for storage and further analysis.
- Samples will be batch processed and analyzed per the procedure outlined in **Appendix E** after the last patient has been enrolled and completed treatment, or sooner if there is

Abbreviated Title: IL-15+Mogamulizumab

Version Date: 11/16/2020

clinical suspicion for anti-IL-15 antibody formation.

5.2.2.6 CCR4 expression (peripheral blood flow cytometry, optional)

- Collect blood in two 10ml sodium heparin (green-top) tubes; gently invert tubes 8-10 times immediately after collection
- Labels listing the patient's name, date of birth, date and time of the blood draw will be affixed to all the tubes by the staff person who obtained the samples.
- Lymphoid Malignancies Branch Clinical Research personnel will arrange for these samples to be delivered to: Flow Cytometry Laboratory, Laboratory of Pathology, NIH Clinical Center [name] for real-time processing; or delivered to: Leidos Biomedical Research, Inc. in Frederick, MD for storage.

5.2.2.7 CCR4 mutation status (peripheral blood, optional)

- Collect blood in two 10ml sodium heparin (green top) tubes; gently invert tubes 8-10 times immediately after collection.
- Labels listing the patient's name, date of birth, date and time of the blood draw will be affixed to all the tubes by the staff person who obtained the samples.
- Lymphoid Malignancies Branch Clinical Research personnel will arrange for these samples to be delivered to: Molecular Diagnostics Section, Laboratory of Pathology, NIH Clinical Center [name] for real-time processing; or delivered to Leidos Biomedical Research, Inc. in Frederick, MD for storage.

5.2.3 Tissue Samples

5.2.3.1 CCR4 expression (tissue IHC) and mutation status

- Archival block(s) or slides (i.e., at least 15 unstained slides, 5-microns) is required at baseline. Patients with prior skin, lymph node, or visceral biopsies performed at NIH or outside institutions must make specimen blocks available to the NCI Laboratory of Pathology for analysis (IHC and mutation testing). If no prior biopsies are available at the time of screening, patients with MF/SS and ATLL with skin involvement will undergo a punch biopsy of a skin lesion, performed by an NIH Clinical Center dermatologist. Patients with lymph node and/or visceral involvement will undergo an 18g core biopsy performed by the Department of Radiology and Imaging Sciences' Interventional Radiologists (IR).
- Prior specimen blocks will be sent to NCI Pathology Department via FedEx. For patients with no prior samples who undergo biopsy as part of screening (if needed for diagnosis) or baseline, core tumor tissue (or bone marrow aspirate/biopsy) samples will be collected and placed in appropriate media (e.g., RPMI 1640 with 10% human serum and antibiotics, normal saline, and/or formalin) and processed per established techniques. As indicated (Sections 5.1 and 5.2) samples will be sent to the Department of Laboratory Medicine (DLM)/ NCI Laboratory of Pathology (LP) for concurrent routine histologic analysis and reporting, IHC testing for CCR4 expression by tumor cells and tumor-associated immune cells in addition to research testing (i.e., [name] Lab).

Abbreviated Title: IL-15+Mogamulizumab

Version Date: 11/16/2020

5.2.3.2 Tissue immune cell subsets and single-cell RNA-sequencing

- Collect 1-3 4mm punch biopsies (skin) or 1-3 18G core biopsies (lymph node/viscera) in RPMI 1640 with 10% human serum and antibiotics or normal saline.
- Lymphoid Malignancies Branch Clinical Research personnel will arrange for the samples to be delivered to NCI LP for processing to a single-cell suspension and storage. Samples will be batch processed by the single-cell sequencing core (NIH Clinical Center [name]).

5.2.4 Other Samples

5.2.4.1 Germline DNA

Germline DNA will be collected by blood, buccal swab, and/or saliva samples (preferred). These will ideally be collected at baseline; however, may be collected at any point on study based on supplies. Standardized, commercial collection kits or tubes will be used (e.g., 1, 5-10 mL K₂EDTA tube for blood; Isohelix SK-1 for buccal swabs; Salviette/Oragene® for saliva). In the case of buccal swabs, two (2) samples may be collected in order to ensure adequate DNA collection.

Lymphoid Malignancies Branch Clinical Research personnel will arrange for these samples to be delivered to Clinical Support Laboratory, Leidos Biomedical Research, Inc. in Frederick, MD to be processed and DNA extracted/isolated per kit instructions and established techniques.

5.3 SAMPLE STORAGE, TRACKING, AND DISPOSITION

5.3.1 General

Samples will be ordered in CRIS and tracked through a Clinical Trial Data Management system. Should a CRIS screen not be available, the CRIS downtime procedures will be followed. Samples will not be sent outside NIH without appropriate approvals and/ or agreements, if required.

All specimens obtained in the protocol are used as defined in the protocol. Any specimens that are remaining at the completion of the protocol will be stored in the conditions described below. The study will remain open so long as sample or data analysis continues. Samples from consenting subjects will be stored until they are no longer of scientific value or if a subject withdraws consent for their continued use, at which time they will be destroyed.

If the patient withdraws consent the participant's data will be excluded from future distributions, but data that have already been distributed for approved research use will not be able to be retrieved.

The PI will record any loss or unanticipated destruction of samples as a deviation. Reporting will be per the requirements of section [7.2](#).

5.3.2 Lymphoid Malignancies Branch – [name] Laboratory

All samples that are noted in Section [5.1](#) to be analyzed by the [name] Laboratory will first be processed and stored at Clinical Support Laboratory, Leidos Biomedical Research, Inc. in Frederick, MD, as per Section [5.3.3](#).

Abbreviated Title: IL-15+Mogamulizumab

Version Date: 11/16/2020

5.3.3 Clinical Support Laboratory, Leidos Biomedical Research, Inc. in Frederick, MD

The Clinical Support Laboratory, Leidos Biomedical Research, Inc.-Frederick, processes and cryopreserves samples in support of IRB-approved, NCI clinical trials. The laboratory is CLIA certified for anti-IL15 and certain cytokine measurements and all laboratory areas operate under a Quality Assurance Plan with documented Standard Operating Procedures that are reviewed annually. Laboratory personnel are assessed for competency prior to being permitted to work with patient samples. Efforts to ensure protection of patient information include:

- The laboratory is located in a controlled access building and laboratory doors are kept locked at all times. Visitors to the laboratory are required to be accompanied by laboratory staff at all times.
- Hard copy records or electronic copies of documents containing patient information are kept in the locked laboratory or other controlled access locations.
- An electronic database is used to store information related to patient samples processed by the laboratory.
- The database resides on a dedicated program server that is kept in a central, locked computer facility.
- The facility is supported by two IT specialists who maintain up to date security features including virus and firewall protection.
- Program access is limited to specified computers as designated by the laboratory director. Each of these computers has a password restricted login screen.
- The database sample entry program itself is accessed through a password protected entry screen.
- Upon specimen receipt each sample is assigned a unique, sequential laboratory accession ID number. All products generated by the laboratory that will be stored either in the laboratory freezers or at a central repository facility are identified by this accession ID.
- Inventory information will be stored at the vial level and each vial will be labeled with both a sample ID and a vial sequence number.
- Vial labels do not contain any personal identifier information.
- Samples are stored inventoried in locked laboratory freezers and are routinely transferred to the NCI-Frederick repository facilities for long term storage.
- Access to stored clinical samples is restricted. Investigators establish sample collections under “Source Codes” and the Principal Investigator who is responsible for the collections specifies who has access to the collection.
- Specific permissions will be required to view, input or withdraw samples from a collection. Sample withdrawal requests submitted to approved laboratory staff by anyone other than the repository source code owner are submitted to the source code owner for approval. The repository facility will also notify the Source Code holder of any submitted requests for sample withdrawal.
- It is the responsibility of the Source Code holder (the NCI Principal Investigator) to ensure that samples requested and approved for withdrawal are being used in a manner consistent with IRB approval.
- The Clinical Support Laboratory does perform testing services that may be requested by clinical investigators including, but not limited to, immunophenotyping by flow cytometry and cytokine testing using ELISA or multiplex platforms.

Abbreviated Title: IL-15+Mogamulizumab

Version Date: 11/16/2020

- When requests are submitted by the NCI investigator for shipment of samples outside of the NIH it is the policy of the laboratory to request documentation that a Material Transfer Agreement is in place that covers the specimen transfer. The laboratory does not provide patient identifier information as part of the transfer process but may, at the discretion of the NCI investigator, group samples from individual patients when that is critical to the testing process.
- The NCI investigator responsible for the sample collection is responsible for ensuring appropriate approvals and/ or agreements are in place, if required, prior to requesting the laboratory to ship samples outside of the NIH.

5.3.4 Hematopathology Section of the Laboratory of Pathology (Tissue samples)

Archival and/or freshly collected and processed tumor tissue may be stored in the Hematopathology Section of Laboratory of Pathology until ready for planned and/or future research assays if the patient has agreed to allowing specimens to be used in future research studies. IRB approval will be obtained before using any samples to conduct studies that are not described within this protocol. Samples will be stored under conditions appropriate to the type of sample and processing (e.g., ambient or frozen).

Tissue that is given to the technician will be assigned an accession number (HP#) in the HP Case Log book; sample tracking also takes place with a FileMaker Pro data base called HP Patient Information and Specimen Inventory. A Patient background sheet may be filled out and filed with any accompanying paperwork, with final reports and any supplemental reports that follow added as completed.

5.4 SAMPLES FOR GENETIC/GENOMIC ANALYSIS

5.4.1 Description of the scope of genetic/genomic analysis

The research correlates for this study are expected to include DNA/RNA sequencing of tumors, including circulating tumor (ct) DNA. In addition, whole exome sequencing may include evaluation for known lymphoma mutations. For any genetic studies performed, the results will be deposited in a database such as dbGaP per NIH requirements. Although there is controlled access to such a database, such a submission carries theoretical risks of revealing the identity of the subject. This is discussed in the consent.

5.4.2 Description of how privacy and confidentiality of medical information/biological specimens will be maximized

Confidentiality for genetic samples will be maintained as described (Section 5.3). In addition, a Certificate of Confidentiality has been obtained for this study.

5.4.3 Management of Results

Subjects will be contacted if a clinically actionable gene variant is discovered. Clinically actionable findings for this study are defined as disorders appearing in the American College of Medical Genetics and Genomics recommendations for the return of incidental findings that is current at the time of primary analysis. (A list of current guidelines is maintained on the CCR intranet: <https://ccrod.cancer.gov/confluence/display/CCRCRO/Incidental+Findings+Lists>).

Abbreviated Title: IL-15+Mogamulizumab

Version Date: 11/16/2020

5.4.4 Genetic Counseling

Subjects will be contacted at this time with a request to provide a blood sample to be sent to a CLIA certified laboratory. If the research findings are verified in the CLIA certified lab, the subject will be offered the opportunity to come to NIH to have genetic education and counseling to explain this result; at the time of any such event(s), these activities will be funded by the NCI/CCR in consideration of the specific circumstances. If the subject does not want to come to NIH, a referral to a local genetic healthcare provider will be provided (at their expense).

This is the only time during the course of the study that incidental findings will be returned. No interrogations regarding clinically actionable findings will be made after the primary analysis.

6 DATA COLLECTION AND EVALUATION

6.1 DATA COLLECTION

6.1.1 Summary

The PI will be responsible for overseeing entry of data into an in-house password protected electronic system (C3D) and ensuring data accuracy, consistency and timeliness. The principal investigator, associate investigators/research nurses and/or a contracted data manager will assist with the data management efforts. All data obtained during the conduct of the protocol will be kept in secure network drives or in approved alternative sites that comply with NIH security standards. Primary and final analyzed data will have identifiers so that research data can be attributed to an individual human subject participant.

All adverse events, including clinically significant abnormal findings on laboratory evaluations, regardless of severity, will be followed until return to baseline or stabilization of event.

Document AEs from the first study intervention, Study Day 1 through 30 days after the last intervention. Beyond 30 days after the last intervention, only adverse events which are serious and related to the study intervention need to be recorded.

End of study procedures: Data will be stored according to HHS, FDA regulations, and NIH Intramural Records Retention Schedule as applicable.

Loss or destruction of data: Should we become aware that a major breach in our plan to protect subject confidentiality and trial data has occurred, this will be reported expeditiously per requirements in Section [7.2.1](#).

6.1.2 Data Collection/Recording Exceptions

6.1.2.1 Abnormal Laboratory Values

An abnormal laboratory value will be considered an AE **only** if the laboratory abnormality is characterized by any of the following:

- Results in discontinuation from the study
- Is associated with clinical signs or symptoms
- Requires treatment or any other therapeutic intervention
- Is associated with death or another serious adverse event, including hospitalization
- Is judged by the Investigator to be of significant clinical impact

Abbreviated Title: IL-15+Mogamulizumab

Version Date: 11/16/2020

- If any abnormal laboratory result is considered clinically significant, the investigator will provide details about the action taken with respect to the test drug and about the patient's outcome.

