CTC V4 Grade	1	2	3	4	1	2	3	4	1	2	3	4
Arthritis						1						
Bladder infection		1										
Chills	1	1				2				2		
Constipation	1								1			
Diarrhea	2				1				1	1		
Dizziness					2							
Dry mouth	1				2							
Dry skin						1						
Edema limbs	1	1										
Fatigue	1	1							2	1		
Fever	2	2			1	1			2	2		
Headache	1				1							
Hypotension		1				1			1			
Nausea	2				2				3			
Pulmonary edema		1										
Rash maculo-papular	2								2			
Vomiting	2				1				2			

Abbreviated Title: IL-15+Mogamulizumab

Version Date: 11/16/2020

Table 5: Laboratory abnormalities possibly, probably, or definitely related to research (5-day CIV cohort) excluding single grade 1 events

	3 µg/kg n=4				4 µg/kg n=3				5 µg/kg n=4			
CTC V4 Grade	1	2	3	4	1	2	3	4	1	2	3	4
Anemia			2			2			1	1	1	
ALT increased	1	1			1	1			3			
AST increased		2			2				4			
Alkaline phosphatase		1			1		1		2	1		
Hyperbilirubinemia	1	1				1			1		1	
Hypoalbuminemia		2			1	1			2	2		
Creatinine increased					1				1	2		
Hyperglycemia										1		
Hypernatremia	2										1	
Hyponatremia	1		1		2				3			
Hypocalcemia	1				1				4			
Hypokalemia	2	1							1		2	
Hypomagnesemia					1				3			
Hypophosphatemia		1	2			2				1	2	
Lymphocytosis				2				2			1	2
Lymphopenia		1				1	1			2	1	1
Neutropenia	1				1		1			1		
Thrombocytopenia		2			2				1	1		
Leucopenia		2				1	1		1	1	1	

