3.1.1 Dose Limiting Toxicity

A dose-limiting toxicity (DLT) is defined as: any grade 3, 4, or 5 toxicity if not incontrovertibly due to disease progression or an extraneous cause, and deemed possibly, probably or definitely related to IL-15 or mogamulizumab by the PI or designee during the first 28 days of treatment, with the following exceptions:

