10 STATISTICAL CONSIDERATIONS

10.1 STATISTICAL HYPOTHESIS

- Primary Endpoint(s):
 - Maximum tolerated dose (MTD) of rhIL-15 administered intravenously for 5 days in combination with mogamulizumab for up to 6 cycles
 - Frequency (number and percentage) of treatment-emergent AEs
- Secondary Endpoint(s):
 - Overall response rate (including CR and PR)

Abbreviated Title: IL-15+Mogamulizumab

Version Date: 11/16/2020

- ORR, TTP, and PFS by CCR4 mutation status (mutated versus wild type) and presenting diagnosis (MF/SS versus ATLL, MF versus SS, acute/chronic versus lymphoma subtype ATLL)
- Duration of response
- Progression-free, event-free, and overall survival
- Changes in percentage and absolute number of peripheral blood lymphocyte subsets
- Quantitation ADCC performed ex vivo on PBMCs obtained from the patients before and during treatment
- Characterization of changes in immune cell infiltrates of tumor deposits by immunohistochemical and molecular analysis of core biopsies obtained before and during treatment

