10.4.2 Analysis of the Primary Endpoints

Safety summaries will include summaries in the form of tables and listings. Reports will include the frequency (number and percentage) of treatment emergent AEs grouped by severity of the AE (per CTCAE, v5.0) and by relationship to study drug (e.g., either rhIL-15, mogamulizumab, or both).

Laboratory shift tables containing counts and percentages will be prepared by treatment assignment, laboratory parameter, and time. Summary tables will be prepared for each laboratory parameter. Figures of changes in laboratory parameters over time will be generated.

Results of vital sign assessments, ECGs, and physical exams will be tabulated and summarized.

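### The laboratory AE rule ignores CTCAE grade, so some Grade 3-4 laboratory values, including possible DLTs, can stay out of the primary AE-frequency endpoint

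*Combined protocol and SAP*

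**What the plan says.** Section 10.1 lists "Frequency (number and percentage) of treatment-emergent AEs" as a primary endpoint beside the MTD. Section 10.4.2 sets out its analysis: "Reports will include the frequency (number and percentage) of treatment emergent AEs grouped by severity of the AE" and by relationship to either drug or both.

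What enters that count is governed by Section 6.1.2.1: "An abnormal laboratory value will be considered an AE" only if it meets at least one of five conditions:

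- it leads to discontinuation from the study;
- "Is associated with clinical signs or symptoms";
- "Requires treatment or any other therapeutic intervention";
- it is associated with death or another serious event;
- "Is judged by the Investigator to be of significant clinical impact".

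Two other sections use a different test. Section 8.1.1 includes an abnormal laboratory finding in its AE definition and attaches no such conditions. Section 3.1.1 defines a DLT by grade and attribution, as "any grade 3, 4, or 5 toxicity if not incontrovertibly due to disease progression or an extraneous cause", subject to listed exceptions. Whether the value was symptomatic or treated matters only inside some of those exceptions.

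Laboratory results are also reported apart from the AE count. Section 10.4.2 plans shift tables, summary tables and figures for laboratory parameters, and Section 10.4.4 promises the type, grade and frequency of toxicities.

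**The concern.** A primary safety endpoint tabulated by CTCAE grade is fed by a recording rule in which grade plays no part. Two patients with the same Grade 4 value can be counted differently, because one was treated and the other was not, or because one investigator thought the value important and another did not. In an open-label trial with a ceiling of 20 patients, a few such decisions can move the Grade 3-4 rate visibly.

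The class of toxicity matters here. The protocol's own 5-day infusion data show severe toxicity only among laboratory values. Those data were reported as "Laboratory abnormalities possibly, probably, or definitely related to research (5-day CIV cohort) excluding single grade 1 events", that is, by grade and attribution with no stated test of clinical significance. An AE table built under Section 6.1.2.1 would not be directly comparable with them.

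The two primary endpoints can also describe one event differently: a DLT for escalation, but not necessarily an AE in the AE table.

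**Working it through.** **No stated figure to reproduce.** The plan does not say how much laboratory toxicity the rule would exclude. What can be done is to count the prior severe entries and apply the rule under stated assumptions.

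**Step 1: count the prior data.** The inputs are Table 5 in Section 1.2.5.1 (3, 4 and 5 mcg/kg; n = 4 + 3 + 4 = 11; CTC v4) and the clinical table printed just before it. The clinical table's title is not in the text available for this review, and I assume it covers the same patients.

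- Clinical table: 60 entries, 0 at Grade 3-4.
- Table 5: 111 entries, 26 at Grade 3-4.

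| Laboratory entry | Grade 3 | Grade 4 | Total |
|---|---|---|---|
| Lymphocytosis | 1 | 6 | 7 |
| Hypophosphatemia | 4 | 0 | 4 |
| Anemia | 3 | 0 | 3 |
| Lymphopenia | 2 | 1 | 3 |
| Hypokalemia | 2 | 0 | 2 |
| Leucopenia | 2 | 0 | 2 |
| Alkaline phosphatase | 1 | 0 | 1 |
| Hyperbilirubinemia | 1 | 0 | 1 |
| Hypernatremia | 1 | 0 | 1 |
| Hyponatremia | 1 | 0 | 1 |
| Neutropenia | 1 | 0 | 1 |
| **Total** | **19** | **7** | **26** |

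So 26 of 26 visible Grade 3-4 entries are laboratory entries.

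**Step 2: apply the rule.** Omitted share = (total − entries that meet a condition) / total. The documents do not say which entries were symptomatic, treated or judged significant, so the strict limits are 0/26 and 26/26. Three illustrative assumptions:

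- **A.** Only the electrolyte entries are treated: 4 + 2 + 1 + 1 = 8 captured.
- **B.** A plus the 3 anemia entries treated: 11 captured.
- **C.** B plus the 2 hepatic entries judged significant: 13 captured.

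| Assumption | Omitted, all entries | Omitted, lymphocytosis set aside (26 − 7 = 19) |
|---|---|---|
| A | 18/26 = 69% | 11/19 = 58% |
| B | 15/26 = 58% | 8/19 = 42% |
| C | 13/26 = 50% | 6/19 = 32% |

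**Step 3: compare with the DLT rule.** The exceptions in Sections 3.1.1.1 and 3.1.1.2 do not list anemia or leucopenia, and the liver-test exception covers Grade 3 only. A drug-related Grade 3 anemia or leucopenia, or a Grade 4 liver test, in the first 28 days is therefore a DLT even if silent and untreated. Under 6.1.2.1 it need not be an AE. The discontinuation condition does not clearly close this gap: it refers to leaving the study, whereas a DLT bears on removal from protocol therapy (Section 3.9.1), which the protocol keeps separate from going off study (Section 3.9.2).

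**The case against.** The strongest reply has four parts.

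1. **Investigator judgement can bring any value in.** A Grade 3-4 value is left out only if it fails all five conditions. A value that ends study drug would hardly be judged unimportant, so a DLT missing from the AE table is unlikely in practice. This stands as a limit on size. It does not make capture uniform, because the judgement has no grade threshold.
2. **The prior data give no patient-level rate.** Entries are not patients, and several cytopenia entries may belong to one person. The grading is CTC v4 against v5.0 here, and the doses were 3 to 5 mcg/kg against 2 and 4 here. Seven entries are lymphocytosis, in keeping with the lymphocyte expansion the treatment seeks. All of this stands, and it is why the percentages are illustrations only.
3. **Severe laboratory values are reported elsewhere.** True, under Sections 10.4.2 and 10.4.4. But the shift tables are specified by treatment assignment, parameter and time, with no stated CTCAE grade or drug attribution, and 10.4.4 names no data source. Neither feeds the AE frequency.
4. **A clinical-significance filter is a legitimate prospective choice for a descriptive endpoint.** It is. The difficulty is that 8.1.1 and 3.1.1 do not share it. For lymphopenia and neutropenia without infection there is no conflict with the DLT rule, since both are excepted.

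A reader might infer that most severe toxicity will go unrecorded, or that the MTD is compromised. The documents support neither. They do not show which prior entries would fail every condition, and DLTs are defined by graded toxicity, not by AE status.

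**Conclusion.** The gap is real but limited. As written, the plan allows an asymptomatic, untreated Grade 3-4 laboratory value that is not judged significant to stay out of a primary endpoint, while another section calls it an AE and a third may call it a DLT. This bears on the kind of toxicity that supplied all 26 visible severe entries in the prior data.

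The size cannot be fixed from the documents. The limits are 0 to 100%. The illustrative 50-69% (32-58% without lymphocytosis) rests on assumptions A to C about treatment and judgement and counts entries, not patients. MTD determination and sample size are unaffected. This is a cheap improvement to ascertainment and consistency, not a flaw that undermines the trial.

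**What to change.** Add one criterion to Section 6.1.2.1: any laboratory value of CTCAE v5.0 Grade 3 or higher, and any value meeting the DLT definition in Section 3.1.1, is recorded as an AE with grade and attribution, whether or not it is symptomatic or treated. Keep the present filter for Grades 1-2, and add a cross-reference so that 6.1.2.1, 8.1.1 and 3.1.1 agree. Expected lymphocytosis can be tabulated on its own line so that it does not dominate the severe-event count.

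The cost is a few more CRF lines per patient. Reported Grade 3-4 AE rates will be higher, which the report should explain. The change affects recording only, not dosing, patient management or sample size.
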